**Table 3-1. Analysis Visit Windows for On-treatment qHBsAg, HBV DNA, ddPCR, CCI Vital Signs and Safety Laboratory Data**

Analysis Visit	Nominal Study Day	Lower Limit	Upper Limit
Baseline	1	(none)	1
Week 1	8	2	11
Week 2	15	12	22
Week 4	29	23	43
Week 8	57	44	71
Week 12	85	72	99
Week 16	113	100	141
Week 24	169	142	211
Week 36	253	212	295
Week 48	337	296	≥ 337

Note: For Group 4, subjects were treated with GS 9992 through Week 12 and continued on NUC afterwards.

**Table 3-2. Analysis Visit Windows for On-treatment Qualitative HBV Serology**

Analysis Visit	Nominal Study Day	Lower Limit	Upper Limit
Baseline	1	(none)	1
Week 12	85	2	127
Week 24	169	128	211
Week 36	253	212	295
Week 48	337	296	≥ 337

Note: For Group 4, subjects were treated with GS 9992 through Week 12 and continued on NUC afterwards.

**Table 3-3. Analysis Visit Windows for On-treatment Electrocardiogram (ECG), and Coagulation**

Analysis Visit	Nominal Study Day	Lower Limit	Upper Limit
Baseline	1	(none)	1
Week 12	85	2	≥ 85

Note: ECGs are to be collected at screening, baseline, Week 12 or Early Discontinuation. For purpose of analysis, baseline value will be the last available value prior to the first dose of any study drug. The Early Discontinuation value will be the last available value on or prior to the last dose date of any study drug + 3 days.

**Table 3-4. Analysis Visit Windows for On-treatment Creatinine Clearance and Body Weight Data**

Analysis Visit	Nominal Study Day	Lower Limit	Upper Limit
Baseline	1	(none)	1
Week 12	85	2	211
Week 48	337	212	≥ 337

**Note:**

- a. For Group 4, subjects were treated with GS 9992 through Week 12 and continued on NUC afterwards.
- b. Creatinine clearance data are to be collected at screening, baseline, Week 12, Week 48 or early discontinuation. For purpose of analysis, baseline value will be the last available value prior to the first dose of any study drug. The Early Discontinuation value will be the last available value on or prior to the last dose date of any study drug + 3 days.

Posttreatment data will be mapped to the posttreatment follow-up (FU) analysis windows, which will be defined by FU Day.

- For Groups 1-3

FU Day = Assessment Date - Last Dose Date of GS-9992 or TAF (whichever comes last)

- For Group 4

FU Day = Assessment Date - Last Dose Date of GS-9992 or Date Subject Discontinued NUC (whichever comes last)

Posttreatment FU analysis windows are presented in [Table 3-5](#) and [Table 3-6](#).

**Table 3-5. Analysis Visit Windows for Posttreatment qHBsAg, HBV DNA, ddPCR, CCI Vital Signs and Safety Laboratory Data**

Analysis Visit	FU Day	Lower Limit	Upper Limit
FU Week 4	29	4	43
FU Week 8	57	44	71
FU Week 12	85	72	99
FU Week 16	113	100	127
FU Week 20	141	128	155
FU Week 24	169	156	≥ 169

**Table 3-6. Analysis Visit Windows for Posttreatment Qualitative HBV Serology**

Analysis Visit	FU Day	Lower Limit	Upper Limit
FU Week 12	85	4	127
FU Week 24	169	128	≥ 169

**3.8.3. Selection of Data in the Event of Multiple Records in an Analysis Window**

Depending on the statistical analysis method, single values may be required for each analysis window. For example, change from baseline by visit usually requires a single value, whereas a time-to-event analysis would not require 1 value per analysis window.

If multiple valid, nonmissing, continuous measurements exist in an analysis window, records will be chosen based on the following rules if a single value is needed:

- In general, the baseline value will be the last nonmissing value on or prior to the first dose date of any study drug, unless specified differently. If multiple measurements occur on the same day, the last nonmissing value prior to the time of first dosing of any study drug will be considered as the baseline value. If these multiple measurements occur at the same time or the time is not available, the average of these measurements will be considered the baseline value.
- For postbaseline values (except for ALT):

The record closest to the nominal day for that visit will be selected.

If there are 2 records that are equidistant from the nominal day, the later record will be selected.

If there is more than 1 record on the selected day, the average will be taken except for qHBsAg (IU/mL) and HBV DNA (IU/mL), HBeAg (IU/mL), HBcrAg (U/mL), HBV RNA (Copies/mL) as for which the geometric mean will be taken.

- For postbaseline ALT values:

The record with the largest value within the same analysis window will be selected

If there is more than 1 record with the largest value, the latest record will be selected.

If there are multiple largest records with the same time or no time recorded on the same day, any one of these measurements can be selected as the analysis value.

If multiple valid, nonmissing, categorical measurements exist in an analysis window, records will be chosen based on the following rules if a single value is needed:

- For baseline, the last available record on or prior to the date of the first dose of any study drug will be selected. If there are multiple records with the same time or no time recorded on the same day, the value with the lowest severity will be selected for safety data (eg, normal will be selected over abnormal for safety ECG findings) and the most conservative value will be selected for efficacy data (eg, negative will be selected over positive for HBeAg and HBsAg whereas positive will be selected over negative for HBeAb and HBsAb).

- For postbaseline values:

The most conservative value (eg, abnormal will be selected over normal for safety ECG) within the window will be selected except for HBV serology (HBsAg, HBsAb, HBeAg, and HBeAb), for which the most favorable value (ie, negative will be selected over positive for HBsAg and HBeAg, whereas positive will be selected over negative for HBsAb and HBeAb) will be selected.

In the event that more than 1 value within a window are the value collected closest to the nominal day will be selected.

If there are 2 records that are equidistant from the nominal day, the later record will be selected.

If there is more than 1 record on the selected day, the latest record will be selected; if these measurements were recorded at the same time or no time recorded, any one of these measurements can be selected as the analysis value.

## 4. SUBJECT DISPOSITION

### 4.1. Subject Enrollment and Disposition

Key study dates (i.e., (first subject screened, first subject enrolled, last subject enrolled/randomized, last subject last visit for the primary endpoint, and last subject last visit for the clinical study report) will be provided. Last subject last visit for the primary endpoint in this study is the last subject who completed Week 12 qHBsAg collection. Last subject last visit for the clinical study report in this study is the last subject who completes TFFU period.

A summary of subject enrollment will be provided by treatment group for each country and investigator within a country and overall. The summary will present the number and percentage of subjects enrolled. For each column, the denominator for the percentage calculation will be the total number of subjects analyzed for that column.

A similar enrollment table will be provided by randomization stratum, ie, HBeAg status (positive, negative). The denominator for the percentage of subjects in the stratum will be the total number of enrolled subjects. If there are discrepancies in the value used for stratification assignment between the IXRS and the clinical database, the value collected in the clinical database will be used for the summary. A listing of subjects with discrepancies in the value of HBeAg used for stratification assignment between the IXRS and the clinical database at the time of data finalization will be provided.

The randomization schedule used for the study will be provided as an appendix to the CSR.

A summary of subject disposition will be provided by treatment group and study overall. This summary will present the number of subjects screened and the number of subjects in each of the categories listed below:

- All Enrolled/Randomized Analysis Set
- Safety Analysis Set
- FAS
- Biomarker Analysis Set
- TFFU Analysis Set
- GS-9992 completion status

Completed GS-9992

Prematurely discontinued GS-9992

- Reason for premature discontinuation of GS-9992
- TAF completion status
  - Completed TAF
  - Prematurely discontinued TAF
- Reason for premature discontinuation of TAF
- TFFU completion status
  - On TFFU
  - Completed TFFU
  - Prematurely discontinued TFFU
- Reason for premature discontinuation of TFFU
- Study completion status
  - On Study
  - Completed study
  - Prematurely discontinued study
- Reason for premature discontinuation of study

For the status of study drug and study completion and the reasons for premature discontinuation, the number and percentage of subjects in each category will be provided. The denominator for the percentage calculation will be the total number of subjects in the Safety Analysis Set corresponding to that column. In addition, a flowchart will be provided to depict the disposition.

The following by-subject listings will be provided by subject identification (ID) number in ascending order to support the above summary tables:

- Reasons for premature study drug or study discontinuation
- Reason for premature discontinuation from TFFU
- Reasons for screen failure (will be provided by screening ID number in ascending order)
- Lot number and kit ID (if applicable)

## **4.2. Extent of Study Drug Exposure and Adherence**

Extent of exposure to study drug will be examined by assessing the total duration of exposure to study drug and the level of adherence relative to the study drug regimen specified in the protocol.

### **4.2.1. Duration of Exposure to Study Drug**

Total duration of exposure to study drug will be defined as last dose date minus first dose date plus 1, regardless of any temporary interruptions in study drug administration, and will be expressed in weeks using up to 1 decimal place (eg, 4.5 weeks). If the last study drug dose date is missing, the latest date among the study drug end date, clinical visit date, laboratory sample collection date, and vital signs assessment date that occurred during the on-treatment period will be used.

The total duration of exposure to GS-9992 and TAF will be summarized using descriptive statistics (n, mean, SD, median, Q1, Q3, minimum, and maximum) and using the number (ie, cumulative counts) and percentage of subjects exposed through the following time periods: Baseline, Week 1, Week 2, Week 4, Week 8, Week 12 for both GS-9992 and TAF, and additionally Week 16, Week 20, Week 24, Week 28, Week 32, Week 36, Week 40, Week 44 and Week 48 for TAF.

A 3-day window is applied to the last planned on-treatment visit to match with the protocol-specified visit window. Summaries will be provided for each treatment group for the Safety Analysis Set.

No formal statistical testing is planned.

### **4.2.2. Adherence to Study Drug**

The presumed number of doses taken by a subject will be determined by the data collected on the drug accountability eCRF using the following formula:

$$\text{Total Number of Doses Administered} \\ \left( \sum \text{No. of Doses Dispensed} \right) - \left( \sum \text{No. of Doses Returned} \right)$$

#### **4.2.2.1. Prescribed Adherence to GS-9992**

The level of prescribed adherence to GS-9992 will be determined by the total amount of study drug taken relative to the total amount of study drug specified by the protocol for a subject who completes treatment in the study.

The level of adherence will be expressed as a percentage using the following formula:

$$\text{Adherence to GS-9992 (\%)} = \left( \frac{\text{Total Amount of Study Drug Taken}}{\text{Total Amount of Study Drug Specified by Protocol}} \right) \times 100\%$$

Note: If calculated adherence is greater than 100%, the result will be set to 100%.

For a record where the number of capsules/tablets returned was missing (with “Yes” answered for “Was bottle returned?” question), it is assumed the number of capsules/tablets returned was 0. If the number of capsules/tablets dispensed was missing or any study drug bottle was not returned or the bottle return status was unknown for the same dispensing date, then the capsules/tables will be treated as not taken.

In this study, the total amount of GS-9992 prescribed for 12 weeks would require 168 capsules for Group 1 (dosed with 2 capsules of GS-9992 25 mg QD); 168 tablets for Group 3 (dosed with 2 tablet of GS-9992 100 mg QD); 84 tablets for Group 4 (dosed with 1 tablet of GS-9992 100 mg QD); 168 tablets for Group 5 (dosed with 2 capsules of GS-9992 200 mg QD) respectively.

Descriptive statistics for the level of prescribed adherence to GS-9992 (n, mean, SD, median, Q1, Q3, minimum, and maximum) along with the number and percentage of subjects belonging to adherence categories (< 80%, ≥ 80 to < 90%, ≥ 90%) will be provided for Group 1, 3, 4 and 5 by treatment group for the Safety Analysis Set. No inferential statistics will be provided.

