#### **4.2.2.2. Adherence to TAF**

The level of adherence to TAF will be determined by the total amount of study drug taken relative to the total amount of study drug prescribed, where each total amount is obtained by summing up the corresponding amount at each dispensing period over all evaluable dispensing periods.

The level of adherence will be expressed as a percentage using the following formula:

$$\text{Adherenceto TAF (\%)} = \left( \frac{\sum \text{No. of Tablets Taken at Each Dispensing Period}}{\sum \text{No. of Tablets Prescribed at Each Dispensing Period}} \right) \times 100\%$$

- 1) Number of tablets taken at a distinct dispensing period is calculated as the minimum of (a) the daily number of tablets prescribed for TAF multiplied by **the duration of treatment** at the dispensing period of the same dispensing date, and (b) the number of tablets taken (number of tablets dispensed minus the number of tablets returned). Total number of tablets taken is determined by summing the number of tablets taken from all evaluable dispensing periods.
- 2) Number of tablets prescribed at a distinct dispensing period is calculated as the daily number of tablets prescribed for TAF multiplied by the duration of treatment at the dispensing period of the same dispensing date. Total number of tablets prescribed is determined by summing the number of tablets prescribed from all evaluable dispensing periods.

**The duration of treatment** at a dispensing period for a study drug is calculated as the minimum of (a) the last returned date of the same dispensing period for the study drug, (b) date of premature discontinuation of the study drug, and (c) **next dispensing date** of the study drug, minus dispensing date of the study drug.

**The next dispensing date** is the following dispensing date of the study drug regardless of the bottle return date.

Note: If calculated adherence is greater than 100%, the result will be set to 100%.

For TAF, a record where the number of capsules/tablets returned was missing (with “Yes” answered for “Was bottle returned?” question); it is assumed the number of capsules/tablets returned was 0. If the number of capsules/tablets dispensed was missing or any study drug bottle was not returned or the bottle return status was unknown for the same dispensing date, then all records for the same dispensing date for that study drug will be excluded from both denominator and numerator calculation.

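### An unreturned GS-9992 bottle is scored as drug not taken against a fixed 12-week total, which can place an otherwise fully adherent subject in the under-80% category

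*SAP*

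**What the plan says.** For GS-9992, SAP 4.2.2.1 defines adherence as the amount taken "relative to the total amount of study drug specified by the protocol for a subject who completes treatment in the study". That denominator is 168 units in Groups 1, 3 and 5 and 84 in Group 4. Results above 100% are set to 100%, and subjects are classed as under 80%, 80 to under 90%, or 90% and over.

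The same section has two rules for incomplete accountability data:

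- If a bottle came back but its contents were not counted, nothing is assumed returned, so the whole bottle counts as taken.
- The other rule ends with "then the capsules/tables will be treated as not taken", and the denominator is not adjusted. It comes into force if the dispensed count is missing, or in the case where "any study drug bottle was not returned or the bottle return status was unknown for the same dispensing date".

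For TAF, SAP 4.2.2.2 uses the same trigger, but all records for that dispensing date "will be excluded from both denominator and numerator calculation". SAP 4.2.2, which precedes both, counts doses taken as dispensed minus returned. The SAP gives no reason for treating the two drugs differently.

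**The concern.** A bottle that does not come back is missing information about dosing. The GS-9992 rule turns it into a definite zero and leaves the denominator whole, so the reported figure can only move down. This runs against the dispensed-minus-returned rule, under which an unreturned bottle counts as taken. It is also the opposite of what the same section does with a returned but uncounted bottle.

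The trigger works at the level of the dispensing date, and each GS-9992 dispensing needs two to four bottles. One lost bottle may therefore wipe out bottles that were returned and counted.

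At stake is how the adherence table is read. PK analysis will not be done (SAP 8), and exposure duration ignores temporary interruptions (SAP 4.2.1), so the pill count is the summary of exposure most sensitive to missed doses. From the table alone, a reader could not tell whether a low value means missed doses, early discontinuation or a lost bottle.

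**Working it through.** **Inputs**

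- Units per day: 2 in Groups 1, 3 and 5; 1 in Group 4 (SAP 4.2.2.1).
- GS-9992 dispensed at Day 1, Week 4 and Week 8 (protocol 6.2.2, 6.3 and Appendix 2): three dispensings of 28 days.
- Bottle sizes: 17 (25 mg capsules), 17 (100 mg tablets), 35 (200 mg tablets) (protocol 5.2.2.1).
- Visit window: ±3 days (protocol 6.3).

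**The SAP's own totals.** 2 × 84 = 168 and 1 × 84 = 84. All four stated group totals are reproduced.

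**One dispensing.** 2 × 28 = 56 units, or 28 in Group 4. Bottles needed: 56/17, rounded up, is 4 (Groups 1 and 3); 28/17 gives 2 (Group 4); 56/35 gives 2 (Group 5).

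**Rule applied to the whole dispensing, subject otherwise fully adherent**

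- One dispensing zeroed: (168 − 56)/168 = 112/168 = 66.7%. Group 4: (84 − 28)/84 = 56/84 = 66.7%.
- Two zeroed: 56/168 = 33.3%.
- Moving the Week 4, 8 and 12 visits within ±3 days changes the period lengths. The lowest case is 25, 34 and 22 days with the middle one lost: 47/84 = 56.0%. The highest is 31, 22 and 34 days with the middle one lost: 65/84 = 77.4%. All are under 80%.

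**Counted drug discarded.** In Group 1, suppose one fully used bottle of 17 is lost. The other three held 51, and 12 came back (4 × 17 = 68 dispensed, 56 taken), so 51 − 12 = 39 units are documented as taken. On this reading those 39 also become zero.

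**Rule applied to the lost bottle only (a fully used bottle)**

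- Groups 1 and 3: (168 − 17)/168 = 151/168 = 89.9%.
- Group 4: (84 − 17)/84 = 67/84 = 79.8%.
- Group 5: (168 − 35)/168 = 133/168 = 79.2%.

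**Dispensed minus returned.** For the same subject, a lost fully used bottle gives 100%. A lost last, part-used bottle adds its unused units (12, 6 or 14): 180/168 = 107.1%, 90/84 = 107.1% or 182/168 = 108.3%, all set to 100%.

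**Affected dispensing removed from both sides.** On schedule, 112/112 = 100% and 56/56 = 100%. At the least favourable visit timing, (47 × 2)/(168 − 56) = 94/112 = 83.9%, still above 80%.

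**Effect on a group summary.** One such subject in a group of 30 adds 1/30 = 3.3 percentage points to the under-80% share and lowers the group mean by 33.3/30 = 1.1 points. In Group 4, with 20 subjects, the figures are 5.0 and 1.7 points.

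**The case against.** Several parts of the opposing case stand.

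- **Scope is not stated.** The TAF rule says explicitly that all records for the date are affected; the GS-9992 rule does not. The date-level trigger favours the whole-dispensing reading, but the bottle-only reading is possible and keeps Groups 1 and 3 at 89.9%.
- **66.7% is not a ceiling.** A reader might infer that it is. Visit timing allows 77.4%. If the other two dispensings were returned uncounted, full bottles are credited: 136/168 = 81.0% (Group 4: 68/84 = 81.0%), or 140/168 = 83.3% in Group 5. The synopsis gives dispensing as Weeks 1-8. If Weeks 1 and 2 were real dispensing dates, losing an early dispensing would cost 7 or 14 days: 77/84 = 91.7% or 70/84 = 83.3%. The synopsis itself refers to Appendix 2, which shows three dispensings.
- **Zero credit is a recognisable conservative convention.** A reader might infer that the rule is simply an error, but the documents do not support that. Exclusion is not neutral either: it overstates adherence if poorly adherent subjects return fewer bottles.
- **The two drugs' measures differ by design.** A reader might infer that the bottle rule is what makes GS-9992 and TAF adherence non-comparable. It is not. A subject who stops both drugs at Week 4 after perfect dosing, with no bottle lost, scores 56/168 = 33.3% for GS-9992 and 100% for TAF.
- **Pill counts are not the only exposure information.** The SAP also plans completion status with reasons, important deviations, adverse events leading to dose modification or interruption, and a by-subject accountability listing in which affected subjects can be found.
- **No loss rate is available.** Protocol 5.5 requires all dispensed product to be returned, so non-return should be the exception.

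None of this explains why one section treats two forms of missing accountability data in opposite ways, or why returned and counted units should be set to zero.

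**Conclusion.** The point holds as a cheap improvement. The GS-9992 rule is an unlabelled worst-case imputation with an unclear scope. It biases a reported number downward and is inconsistent with SAP 4.2.2.

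The 66.7% rests on three equal on-schedule dispensings, one of them affected, full adherence otherwise, complete counts for the other two, and the whole-dispensing reading. Under those conditions apart from visit timing, the under-80% category holds throughout the windows. On the bottle-only reading with a fully used bottle lost, Groups 4 and 5 still fall just below 80%, while Groups 1 and 3 do not. How many subjects would be affected cannot be derived from the documents.

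The consequence stays within the descriptive adherence summary. A reader might infer that efficacy or the analysis populations are touched, but no efficacy estimate uses adherence, and both the Full and Safety Analysis Sets require only one dose.

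**What to change.** In SAP 4.2.2.1:

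1. Keep the protocol-total measure, but for a dispensing that was made and cannot be evaluated, remove its protocol amount (56 units, or 28 in Group 4) from both numerator and denominator. Report a subject with no evaluable dispensing as not evaluable.
2. Show the current rule as a second line, labelled worst case.
3. State whether the rule acts per bottle or per dispensing.
4. Report the number of subjects affected in each group.

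The cost is one extra derivation and a few lines of text. The per-dispensing amounts must be written in, because the section gives only 12-week totals. The exclusion line may overstate adherence if non-return goes with poor adherence, which is why the worst-case line stays. The change does not make GS-9992 and TAF adherence fully comparable, since their denominators would still differ.

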#### **4.2.2.2. Adherence to TAF**

The level of adherence to TAF will be determined by the total amount of study drug taken relative to the total amount of study drug prescribed, where each total amount is obtained by summing up the corresponding amount at each dispensing period over all evaluable dispensing periods.

The level of adherence will be expressed as a percentage using the following formula:

$$\text{Adherenceto TAF (\%)} = \left( \frac{\sum \text{No. of Tablets Taken at Each Dispensing Period}}{\sum \text{No. of Tablets Prescribed at Each Dispensing Period}} \right) \times 100\%$$

- 1) Number of tablets taken at a distinct dispensing period is calculated as the minimum of (a) the daily number of tablets prescribed for TAF multiplied by **the duration of treatment** at the dispensing period of the same dispensing date, and (b) the number of tablets taken (number of tablets dispensed minus the number of tablets returned). Total number of tablets taken is determined by summing the number of tablets taken from all evaluable dispensing periods.
- 2) Number of tablets prescribed at a distinct dispensing period is calculated as the daily number of tablets prescribed for TAF multiplied by the duration of treatment at the dispensing period of the same dispensing date. Total number of tablets prescribed is determined by summing the number of tablets prescribed from all evaluable dispensing periods.

**The duration of treatment** at a dispensing period for a study drug is calculated as the minimum of (a) the last returned date of the same dispensing period for the study drug, (b) date of premature discontinuation of the study drug, and (c) **next dispensing date** of the study drug, minus dispensing date of the study drug.

**The next dispensing date** is the following dispensing date of the study drug regardless of the bottle return date.

Note: If calculated adherence is greater than 100%, the result will be set to 100%.

For TAF, a record where the number of capsules/tablets returned was missing (with “Yes” answered for “Was bottle returned?” question); it is assumed the number of capsules/tablets returned was 0. If the number of capsules/tablets dispensed was missing or any study drug bottle was not returned or the bottle return status was unknown for the same dispensing date, then all records for the same dispensing date for that study drug will be excluded from both denominator and numerator calculation.

Descriptive statistics for the level of prescribed adherence to TAF (n, mean, SD, median, Q1, Q3, minimum, and maximum) along with the number and percentage of subjects belonging to adherence categories (< 80%, ≥ 80 to < 90%, ≥ 90%) will be provided for Group 1, 2, 3 and 5 by treatment group for the Safety Analysis Set. No inferential statistics will be provided.

A by-subject listing of study drug administration and drug accountability will be provided separately by subject ID number and visit (in chronological order).

